8.3.1 Datasets to be analysed

Regression analyses of the primary outcome and secondary outcomes may suffer from missing data, which may cause bias and loss of information in analyses that are restricted to study participants with complete data ("complete-case analyses"). To appropriately account for missing data in advanced regression analyses we will use multiple imputation techniques as well as an iterative imputation method (missForest) based on a random forest (33, 34).

Due to the relatively high anticipated sample size, the analysis will be split up into specific sub-groups (e.g. completeness of lesion, para-/tetraplegia, type of pneumonia). For mortality flexible parametric modeling of survival data) and other secondary outcome analyses will be performed Handling of missing data

8.3.2 Ancillary analysis

For primary outcome: if distribution of ROC is not normal, a non-parametric approach can be used as part of sensitivity analysis (Pepe 2013).

Further, a comparison of results from imputed data (main analysis) with results of unimputed data (i.e, including complete data sets only) will be performed.

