3.3 Risk-Benefit Assessment (HRA Art. 12; HRO Art. 15)

Patients have to perform a maximum of 4 measurement sessions (dependent on the time of rehabilitation) with 40 min of measurements each. Therefore the time needed for this study will not negatively influence rehabilitation of included patients. Lung function and respiratory muscle strength measurements are non-invasive and also part of clinical routine. Safety of these measurements is very high and to the best of our knowledge we are not aware of any adverse events due to such measurements.

Potential benefit of project result:

Increased knowledge on determinants and effects of pneumonia will help adapt rehabilitative strategies/therapy to prevent patients from pneumonia and thereby also increase quality of life of the patients and life expectancy.

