6.3 Criteria for withdrawal / discontinuation of participants

Reasons for which a participant needs to discontinue from the project:

- withdrawal of informed consent
- non-compliance
- medical complications which do not allow measurements of this study
- death

In case of drop-out, the already recorded data will be used for further analyses. All data of drop-out patients will be anonymized after analysis.

We will report all reasons for withdrawal of the participants and compare the reasons qualitatively.

The study will not be stopped in case of futility, unless CTU Nottwil during the course of safety monitoring advices otherwise. In this case, CTU Nottwil will discuss potential stopping for futility with the study investigators group.

The final decision to terminate the study is taken by the Principal Investigator of the study.

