7.1 Project flow chart(s) / table of procedures and assessments

7.2 Assessments of primary endpoint/outcome

The primary endpoint of this study is the diagnostic accuracy of inspiratory muscle strength for predicting or excluding clinical pneumonia. Diagnostic accuracy of positive and negative results will be evaluated by the area under the receiver operating characteristic (ROC) curve, which provides an operational measure of the intrinsic ability of the diagnostic test by offsetting the true positive rate against the false positive rate (13). Based on our previous evidence, MIP was defined as the primary diagnostic lung parameter (14). The potential additive diagnostic value of various other lung parameters, including forced vital capacity (FVC), forced expiratory volume in 1 second (FEV₁), peak expiratory flow (PEF), peak cough flow (PCF) and maximum expiratory muscle strength (MEP) will also be investigated. The two measures for the primary endpoint, maximal inspiratory pressure (MIP) and the event of clinical pneumonia, are assessed as follows.

Inspiratory muscle strength will be measured using a hand-held respiratory pressure meter (Micro RPM, Micro Medical, Hoechberg, Germany) by an independent study nurse of each participating study site. All measurements will be performed with the patients sitting upright in their own wheelchair. Patients have to breathe through a mouthpiece while wearing a nose clip. Each measurement will be repeated three times. The greatest value of each parameter will be used for analysis (15).

For each event of pneumonia the following information will be recorded: date of event; duration of event; physician diagnosed; and type. The differentiation of the type of pneumonia is important and will be evaluated using patients medical records data following the pneumonia flow diagram of "Disease and Control Prevention / National Healthcare Safety surveillance definition of health care—associated infection and criteria for specific types of infections in the acute care setting" (16). To determine the type of pneumonia the methods x-ray, signs and symptoms and the laboratory are used. Finally four different types of pneumonia can be diagnosed.

Pneumonia 1: clinically defined pneumonia

Pneumonia 2: pneumonia with common bacterial or filamentous fungal pathogens and specific lab findings

Pneumonia 3: pneumonia with viral and other uncommon pathogens and specific lab findings Pneumonia 4: pneumonia in immunocompromised patients

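### MIP tests missing because the patient is too ill or weak are imputed like any other missing value, and agreement with the complete-data result cannot be relied on as reassurance

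*Combined protocol and SAP*

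**What the plan says.** Section 8.3.1 (Datasets to be analysed) covers missing data in the regression analyses of primary and secondary outcomes: "we will use multiple imputation techniques as well as an iterative imputation method (missForest) based on a random forest". It does not separate reasons for missingness, list the variables in the imputation model, or state an assumption about the missing-data mechanism. Section 8.3.2 (Ancillary analysis) makes the imputed result the main one and adds that "a comparison of results from imputed data (main analysis) with results of unimputed data (i.e, including complete data sets only) will be performed". The other item there, a non-parametric ROC approach, concerns distributional form and not the imputation.

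Two other sections make illness-related missing tests foreseeable. Section 6.3 lists among the reasons for discontinuation "medical complications which do not allow measurements of this study", and section 7.2 specifies that "All measurements will be performed with the patients sitting upright in their own wheelchair". Section 6.3 also says "In case of drop-out, the already recorded data will be used for further analyses" and "We will report all reasons for withdrawal of the participants and compare the reasons qualitatively", but links neither statement to the imputation. Section 8.3.2 (Advanced regression modelling), under sampling and attrition bias, plans to examine selective dropout against baseline characteristics, with inverse probability weighting as an option.

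**The concern.** A patient who cannot sit up or cannot perform the manoeuvre is likely to be among the weakest. Standard multiple imputation and missForest fill that patient's MIP from patients who could be tested, so the filled-in value will tend to be too high. A complete-data analysis drops the same patient. Both lose the low tail of MIP, which lies mostly among pneumonia cases, and both understate discrimination. If the two results then agree, the report may present this as evidence that missing data did no harm. What is at stake is the primary AUC and, by the same mechanism, any low-MIP cut-off derived from it.

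**Working it through.** **The plan's own figures.** Section 8.1: 250 per year × 2.5 years = 625; 625 × 0.40 = 250 cases. Reference AUC 0.86; AUC change to be detected 0.05 to 0.07. The documents give no rate of missing tests.

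**Why the two results can agree.** Suppose the imputation model knows only pneumonia status. The imputed values in each group are then draws from that group's observed MIP distribution, so the completed data reproduce the complete-case AUC. A gap can appear only if other variables carry information on the missing MIP.

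**Simulation.** 625 patients, 250 cases. MIP is normal with SD 1 in each group, and cases are lower by √2 × Φ⁻¹(0.86) = 1.414 × 1.080 = 1.53. Missingness has a logit slope of 1.5 or 3 per overall SD of MIP, lower MIP being more often missing. Multiple imputation uses a normal model with outcome, one auxiliary variable and their interaction (5 imputations, 200 replicates). Assumptions not in the documents: 10-30% missing, both slopes, and a within-group correlation of the auxiliary variable with MIP of 0.3 (weak) or 0.6. missForest and repeated visits were not modelled in this simulation.

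Weak auxiliary variable (0.3), bias against full data in brackets:

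| Missing | Slope | Full data | Complete data | Imputed | Gap |
|---|---|---|---|---|---|
| 10% | 1.5 | 0.859 | 0.848 (−0.011) | 0.849 (−0.010) | 0.001 |
| 10% | 3 | 0.861 | 0.839 (−0.022) | 0.841 (−0.020) | 0.002 |
| 20% | 1.5 | 0.861 | 0.844 (−0.017) | 0.845 (−0.016) | 0.001 |
| 20% | 3 | 0.859 | 0.821 (−0.038) | 0.820 (−0.039) | 0.001 |
| 30% | 3 | 0.860 | 0.809 (−0.051) | 0.807 (−0.053) | 0.002 |

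With the stronger auxiliary variable (0.6) at 10-20% missing, imputation gives 0.837 to 0.854 (bias −0.005 to −0.023) and complete data 0.822 to 0.848. The gap is 0.006 to 0.015: visible, but it does not measure the remaining bias. If missingness is random or explained by observed data, imputation bias is at most 0.002.

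**What a shift analysis shows.** Lowering the imputed values of the missing tests by a fixed number of within-group SDs, over all twelve combinations (three missing rates, two slopes, two correlations):

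| Handling | AUC range (truth 0.86) |
|---|---|
| No shift | 0.807-0.854 |
| 0.5 SD | 0.842-0.859 |
| 1.0 SD | 0.857-0.862 |
| 1.5 SD | 0.849-0.862 |
| Lowest rank for all | 0.795-0.856 |

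The shift exposes a dependence that the planned comparison misses. That 1 SD comes closest follows from these scenarios and is not a recommendation. Lowest rank and unshifted imputation both lie below the truth, so together they do not bracket it.

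**The case against.** The strongest reply is that the plan measures MIP up to four times, and a MIP from another visit is a much better auxiliary variable than the weak one above. With an assumed within-group correlation of 0.8 and slope 3, at 5/10/15% missing, imputation gives 0.859/0.856/0.853 and complete data 0.849/0.839/0.830. The bias is then at most 0.007 and the gap 0.010 to 0.023, so the planned comparison does move. This stands, with two limits: the plan does not say that other visits enter the imputation model, and patients with no MIP at any visit gain nothing.

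Second, the complete-data comparison is not the only safeguard. Withdrawal reasons are reported and selective attrition is examined, with optional weighting. That is correct. But the attrition steps rest on baseline or observed data and the reasons are compared only qualitatively, so none of them tests dependence on the unseen MIP.

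Third, size. By the Hanley-McNeil formula the standard error of an AUC of 0.86 with 250 cases and 375 non-cases is about 0.016, so a bias of 0.01 is within sampling noise. Excluding patients on 24-hour ventilation also removes some of the untestable. Both points limit how much may be lost; neither shows that the planned check works.

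A reader might also infer that the plan will impute values after discharge or death, or that its complete-data analysis keeps only patients with all four visits. The documents state neither. Section 3.3 says "Patients have to perform a maximum of 4 measurement sessions (dependent on the time of rehabilitation"), so a visit that never fell due need not count as missing. T4 is tied to discharge, so early discharge removes T2 or T3 and not the final test. Random-effects models accept unequal numbers of visits, and the mortality analysis treats competing events separately. These are matters to clarify.

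**Conclusion.** The concern holds in limited form. The plan foresees MIP tests that cannot be done for medical reasons, has no rule by reason, and has no analysis that departs from ordinary imputation for them. When low MIP drives the missingness and other information on it is weak, imputed and complete-data AUCs are both too low by about 0.01 to 0.04 at 10-20% missing and differ by 0.001 to 0.002. In the most extreme scenario (30% missing, steep slope) the bias reaches about 0.05, the lower end of the change the study is sized to detect. All of this rests on assumed missing rates and slopes.

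The stronger statement, that the planned comparison can never reveal the bias, is not supported, because informative auxiliary data open a gap. The supported conclusion is that agreement between the two results is not evidence against bias. How far the primary result is exposed also depends on which MIP visit enters the ROC analysis, which the plan does not state.

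**What to change.** - Record a reason for every MIP not obtained: unable, refused, missed, discharged, died. The field should exist before recruitment starts, since reasons are hard to reconstruct later.
- Include MIP from other visits in the imputation model.
- Add to section 8.3.2 (Ancillary analysis) a delta-adjusted (tipping-point) analysis that shifts imputed MIP downward for tests coded as unable, over a stated range such as 0 to 1.5 SD, with the SD defined. Lowest rank may be shown as an extreme scenario, not as a bound.
- Keep the complete-data comparison as supplementary.
- As a clarification, state that visits after discharge or death are not imputed.

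The cost is one extra field and one extra analysis. The correct shift is unknown, so the result shows how far the conclusion depends on it and does not replace the main estimate.

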8.3.3 Deviations from the original statistical plan

The analysis protocol will be updated accordingly if needed.

9. DATA AND QUALITY MANAGEMENT

(HRO Art. 5, 25-27, Annex 2/1.7)

9.1 Data handling and record keeping / archiving (HRO Art. 5, 26, 27, Annex 2/1.7)

The secuTrial[®] data management system (iAS, Berlin, Germany), a web-based data capture and management system, will be used. The system is hosted on a server of the Swiss Paraplegic Centre. The project set-up and eCRFs will be tested by the Data Manager of the Swiss Paraplegic Center, Clinical Trial Unit prior to the release into the productive environment using a custom testing protocol. Every staff member is authorized for any CRF entry and by initials noted on the CRF the investigator can be subsequently identified. The data on the CRF will later be entered in the secuTrial[®] database (iAS, Berlin, Germany).

One person will enter the data from the CRF paper form into the secuTrial[®] database. A second person will control the correctness of the data in the secuTrial[®] and the principal investigator will finally release the data for archival storage.

The Clinical Trial Unit will only give access to 2 people: Person A will get access for data entering and controlling and the local investigator (Person B) for data release.

Plausibility rules will be established in the data capture system to promote data quality. Furthermore, data will be reviewed and verified prior to data entry completion.

Encrypted data will be exported from the data management system for analysis in statistic software.

9.2 Confidentiality, Data Protection (HRO Art. 5)

Project data will be handled with uttermost discretion and only be accessible to authorised personnel. Direct access to source documents will be permitted for purposes of monitoring, audits or inspections. The data management system allows to define roles for data entry, verification, validation and management. An audit trail documents all entries and changes made in the system and by whom. Personal data of participating subjects which allow to identify an individual, will not be stored on a server or personal computer, nor will any names of subjects be transmitted to the main study center in Nottwil. These data will be printed on paper and stored in a locked data storage room with limited access in each participating center. An anonymous identification number will allow to connect the data entered in the system, but only by each center for their own subjects. Only anonymous data will be stored in the electronic data capture and management system. Encrypted data will be exported from the data management system for analysis in statistic software.

For data verification purposes, authorised representatives of a competent authority (e.g. an ethics committee) may require direct access to parts of the medical records relevant to the project, including participants' medical history.

9.3 Coding (HRO Art. 25-27)

The secuTrial[©] (iAS, Berlin, Germany), a web-based data capture and management system, will be used. The system is hosted on a secure hospital server. Personal data, which allows to identify an individual, will not be stored on a server or personal computer. These data will be printed on paper and stored in a locked data storage room with limited access in each single site where the data are assessed. An anonymous identification number will allow to connect the data entered in the system with an individual. Only anonymous data will be stored in the electronic data capture and management system.

9.4 Archiving and Destruction

During the study the respective data will be archived in each single study site on paper and as electronic data in the Swiss Paraplegic Centre Nottwil.

During the course of the study, the individuals mentioned in this application will have access to the data according to their pre-defined roles. After termination of the study and archiving of the data, only the Principal Investigator and secuTrial[®] Data Manager will have access to the data. The Data Manager will only have access to the encrypted data.

A back-up system is set in place. It is maintained and controlled by the IT department of the Swiss Paraplegic Centre. Electronic data will be stored in an electronic archive maintained and controlled by the IT department of the Swiss Paraplegic Centre. Electronic data will not be deleted. Source data and

identification data will be stored in a locked archive room with limited access for a minimum of 15 years.

10. PUBLICATION AND DISSEMINATION POLICY

(HRO Art. 15j; STROBE 22; HRO Annex 2/1.10)

10.1 Publication of results

The plans are to write three papers about the topic "Inspiratory muscle strength and respiratory complications after spinal cord injury: a multicenter, prospective cohort study" in 2019 and publish the results in peer reviewed journals. The main topics of these papers should focus on:

- Diagnostic accuracy of inspiratory muscle strength for prediction of pneumonia
- Mortality due to pneumonia and associated factors
- Determinants of pneumonia after SCI (multivariate modelling)

The results can be presented in different conferences e.g. dmgp or ISCoS. The authorship will be arranged in advance as follows, the first author on the publications will be [name] and the senior author will be [name] [name]. Other persons with substantial contributions will be mentioned in-between according to guidelines for publishing of the selected journal. The publications will be also used for obtaining a PhD-degree ([name]).

Local investigators will be included in the discussion of results and publication process of all publications from this project. All local investigators will co-author all publications from this project and therefore will all have to approve at least the last version of every publication.

10.2 Data sharing

In general, only the study investigators have access to the full study dataset in order to ensure that the overall results are not disclosed by an individual study site prior to the main publication. Site investigators are allowed to access the full dataset if a formal request describing their plans is approved by the study investigators. All local data belong to the local centers and will only be transferred coded to the study center.

11. FUNDING AND SUPPORT

(HRO Art. 15j; STROBE 22; HRO Annex 2/1.10)

The main financial support (210'000.- Euro) for the project will be given from the Foundation "Wings for life", Salzburg, Austria.

Wings for life Address: [name], Austria Email: [contact] [contact] [contact]

Additionally, this project is also a "nested project" of the SwiSCI cohort study of the Swiss Paraplegic Research. Therefore, parts of the costs for the Swiss Centers of the study will be covered by a 'SwiSCI-Nested project Start-up Grant' (43'000.- SFr.) from the Swiss Paraplegic Research.

(HRO Annex 1; HRO Annex 2/1.6)

n a

14. APPENDICES

none
